7.1.1. Prior Medications

The total number of prior medications and the number and percentages of subjects with at least one prior medication will be summarized. The number and percentages of all prior medications will be summarized and listed by drug class and preferred term. All summaries will be performed using the FAS.

7.1.2. Concomitant Medications

The total number of concomitant medications and the number and percentages of subjects with at least one concomitant medication will be summarized. The number and percentages of all concomitant medications will be summarized and listed by drug class and preferred term. All summaries will be performed using the FAS.

7.2. Study Treatments

For Ad-RTS-hIL-12, cemiplimab and veledimex, separate summaries will be provided for details in administration using descriptive statistics based on FAS. All administration details will be presented in a listing.

7.2.1. Extent of Exposure

Details of study drug administration and dose modifications will be listed as follows.

7.2.1.1. Ad-RTS-hIL-12

Total volume received, number of sites and whether the dose was modified will be tabulated.

7.2.1.2. Veledimex

The total dose received (mg) for each study treatment will be calculated based on the Drug Accountability CRFs including the oral dosing diaries. Dosing details are summarized per subjects for each dosing cohort. Dose and dose modifications per subject treated will be listed. The number of doses received will be tabulated.

Subject veledimex dosing compliance will be determined for each subject as the total number of tablets dispensed minus the total number of tablets reported as not taken, divided by the total number of tablets dispensed, multiplied by 100.

- Subgroups for dosing compliance may be explored (e.g. compare subgroup of subjects who are 100% (80%) dosing compliant with subgroup of subjects <100% (<80%) dosing compliant).
- Extent of exposure will not be calculated for Ad-RTS-hIL-12 as it will be administered only on Day 0.

7.2.1.3. Cemiplimab and Veledimex, Duration of Exposure

For cemiplimab and veledimex, duration of exposure is defined as the total number of days a subject is exposed to any study drug and will be presented as the total number of days from the first dose date (Day -7 for cemiplimab and Day 0 for veledimex) to the last dose date (date of last dose minus the date of first dose + 1) as recorded on the End of Treatment page on the CRF. If the last dose date on the End of Treatment page is missing, or if a subject is lost to follow-up, but the drug accountability log confirms that the subject has taken study drug, the visit date following the last completed drug accountability log will be used.

- The duration of exposure to study drug will be summarized for cemiplimab and veledimex for all subjects in the FAS.
- The total dose for each study drug will be summarized for cemiplimab and veledimex for all subjects in the FAS.
- A summary of each subject's exposure will be presented in a listing.

7.2.2. Treatment Compliance and Modifications

For Ad-RTS-hIL-12 and cemiplimab, the number and proportion of subjects receiving treatment will be summarized at each scheduled dosing visit.

For veledimex, compliance will be calculated for each subject by making the determination whether a subject takes all doses of study drug as instructed. The number of capsules taken will be calculated by subtracting the number of capsules returned from the number of capsules dispensed. The overall study drug compliance (%) will be calculated by dividing the total number of capsules taken during subject's study period by the total number of capsules expected to be received based on the schedule of events and then multiplying by 100.

Compliance (%) = [(total no. of capsules dispensed – total no. of capsules returned) / (No. of days in interval *No. of capsules prescribed per day)] * 100.

Summary statistics on percentage of veledimex compliance as well as the number and percentage of subjects in each compliance category (<80%, 80-100% compliant) will be presented overall.

A subject is considered compliant to veledimex if overall study drug compliance is greater than or equal to 80%. A categorical summary of whether subjects were compliant (yes/no) will be presented.

Percentages will be calculated out of the number of subjects who were dosed in the FAS.

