Thyroid Panel: free triiodothyronine (FT3), free thyroxine (FT4), and thyroid-stimulating hormone (TSH).

^P Standard 12-lead ECG single measurement at each time point. The Day 0 testing should be obtained prior to veledimex dosing.

⁹ Eligibility must be confirmed within 24 hours prior to dosing with cemiplimab-rwlc. In the event of toxicities likely related to cemiplimab-rwlc, the PI and the Medical Monitor will individualize the management of cemiplimab-rwlc dosing in general accordance with the Investigator's Brochure. Doses must be at least 21 days apart. Delays of up to 14 days are acceptable for toxicity, in consultation with the medical monitor.

¹ Ad-RTS-hIL-12 intratumoral injection should be administered by freehand injection. Subjects must be instructed to maintain adequate oral hydration during the Treatment Period; sites must closely monitor subjects' hydration status. Because of the potential for toxicity (e.g., fevers, chills, fatigue, and dehydration), administration of prophylactic antipyretics is recommended after injection of Ad-RTS-hIL-12.

⁵ Each subject will be carefully monitored for any local reactions and/or hypersensitivity reactions following the Ad-RTS-hIL-12 injection and velevidex administration. Subjects should be instructed to call the clinical site if headache, hemiparesis, seizure, or other local reactions develop anytime and especially between study visits.

[†] The first post-resection veledimex dose will be given on the next day, designated as Day 1, under supervision of the clinical staff to ensure there are no difficulties swallowing the capsule. Subsequent veledimex doses are to be taken once daily, in the morning and within 30 minutes of a regular meal.

^u The Day 3 dose should be held until Day 3 labs have been reviewed. Subjects should not be dosed unless lymphocyte counts, platelet counts, and liver function tests have changed by $\leq 20\%$ from baseline values and the Grade of any abnormality has not increased. Medical monitor consultation is then advised.

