10.5. Monitoring of Subject Adherence and Managing Missed Doses

10.5.1. Veledimex

The first veledimex dose following Ad-RTS-hIL-12 injection is expected to be administered when the subject is at the clinical site, under careful medical supervision by the clinic staff to ensure that the subject does not have difficulty swallowing the capsules. Thereafter, subjects may be allowed to self-administer the remaining once daily doses as described. Subjects are to be instructed to take the appropriate number of capsules in the same way for each of the remaining treatment period days and may be reminded to do so by phone on non-visit days.

Subjects should NOT make up any missed doses.

Subjects should be instructed to document veledimex dosing compliance in a subject diary, including the time subject took the once daily dose, the time subject ate breakfast, the number of capsules taken, whether subject missed any veledimex doses, and the study day and reason for any missed doses. Study drug container(s) with any remaining capsules should be returned to the study staff on Day 15, so that staff can properly assess dose compliance.

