10.10. Dose Modifications and Dose Delays

Veledimex dose delays and dose reductions for individual subjects will be allowed in the event of an adverse event, according to the criteria shown in Table 2.

Table 2: Criteria for Dose Delay and Dose Reduction of veledimex

Adverse Reaction	Severity ²	Veledimex Dosage Modifications ¹
Immediately life-threatening/ Potentially-Fatal Severe Adverse Reactions		
Any non-hematologic AE ³	Grade 4 non-hematologic adverse event at least possibly related to study drug, that is considered by the treating physician to be immediately life-threatening, and results in emergent medical and/or surgical intervention	Discontinue
Other Severe Adverse Reactions		
Cytokine Release Syndrome	Grade 3 or higher (per the Ziopharm Working Definition of Cytokine Release Syndrome)	Withhold ⁴
Any non-hematologic AE ^{3, 5} (except brain edema)	Grade 3 or higher non-hematologic adverse event that is at least possibly related to study drug and persists at least 3 days	Withhold ⁴
Cerebral edema ⁵	Grade 3 or higher	Withhold ^{4, 6}
Thrombocytopenia	Grade 3 or higher thrombocytopenia (< 50,000/mm ³) at least possibly related to study drug	Withhold ⁴
Lymphopenia or other hematologic toxicity	Grade 4 or higher lymphopenia or other hematologic toxicity (except thrombocytopenia)	Withhold ⁴
Increased transaminitis ⁸	Grade 3 or higher increase in ALT or AST	Potentially Withhold ⁷

1. These recommendations are for general guidance only. Treating physicians should manage patients according to their clinical judgement, as informed by institutional guidelines, best practices and these guideline recommendations.
2. Toxicity as graded per National Cancer Institute Common Terminology Criteria for Adverse Events, Version 5.0.
3. Nausea and vomiting will not be considered in this category unless at least Grade 3 or 4 and refractory to antiemetics (i.e., defined as symptoms not mitigated by maximal medical support as directed by the Investigator (per institutional guidelines) in consultation with the Sponsor Clinical Medical Monitor).
4. Withhold the next and any successive doses of veledimex while the Grade 3 or 4 toxicity persists. Veledimex dosing may resume, after discussion with the Sponsor Clinical Medical Monitor, in subjects with rapid and substantial reversal of toxicity, either spontaneously or following appropriate medical treatment. The Sponsor Clinical Study Coordinator will be notified in advance of veledimex dosage modifications.

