4.7.3. Relevant Protocol Deviations (RPD)

Originally, relevant deviations from the study protocol were to be documented and accounted for in presenting the data listings and descriptive statistical analyses. Any changes from planned protocol-specified analyses were to be defined in the SAP and reported in the CSR. Instead, protocol deviations will not be produced by Biostatistics. Instead, protocol deviations will be described with an in-text table as applicable in the final CSR. The relevant protocol deviations are described in the [Table 2](#) below.

Table 2: List of Relevant Protocol Deviations

Number	RPD Criteria
1	Poor treatment compliance for either cemiplimab or veledimex (less than 80% of expected total dose of either treatment)
2	Taking prohibited concomitant medication including CYP3A4 inhibitor
3	Others

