8.2.1. Assumption Testing

No assumption check is planned for the Kaplan-Meier method.

Patient Characteristic Subgroup Factors

Among the patient factors to be explored are the following patient derived variables.

Age category

- <65 vs ≥ 65

Gender

- Female vs Male

MGMT

- unmethylated vs methylated

Hispanic or Latino

- yes=1 vs no=0

Race

- White vs not White

IDH

- wild-type vs mutated

Prior Steroid

- yes=1 vs no=0

Enhanced Lesion

- unifocal vs Multifocal

Number of Lesions at Entry

- 1 vs > 1

KPS Screening, N (%)

- ≥ 70 to 90 vs ≥ 90

veledimex Dosing Compliance

- $<100\% (<80\%)$ vs $100\% (\geq 80\%)$

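### The SAP's veledimex compliance formula counts doses held on protocol instruction as missed, so a hold of four or more of 15 doses is labelled poor compliance

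*SAP*

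**What the plan says.** **Definition and denominator.** SAP Section 7.2.2 starts from a determination of "whether a subject takes all doses of study drug as instructed". It then takes capsules dispensed minus capsules returned and divides this "by the total number of capsules expected to be received based on the schedule of events and then multiplying by 100". The formula displayed below that text has a denominator of days in the interval times capsules prescribed per day, with the interval undefined. A subject is compliant at 80% or more.

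**A second formula.** SAP Section 7.2.1.2 divides by tablets dispensed instead, and adds: "Subgroups for dosing compliance may be explored".

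**Where the score is used.** SAP Section 4.7.3, Table 2, item 1 lists as a relevant protocol deviation: "Poor treatment compliance for either cemiplimab or veledimex (less than 80% of expected total dose of either treatment". That item covers both drugs; this point concerns veledimex only. The list of patient factors printed under SAP Section 8.2.1, within the OS analysis, ends with "veledimex Dosing Compliance", split at 100% with 80% in brackets.

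**Instructed omissions.** Protocol Section 10.10, Table 2, note 4 says: "Withhold the next and any successive doses of veledimex while the Grade 3 or 4 toxicity persists". The same table discontinues veledimex for certain life-threatening Grade 4 events. On Day 3 the dose waits for laboratory review: "Subjects should not be dosed unless lymphocyte counts, platelet counts, and liver function tests have changed by" no more than 20% from baseline, with no rise in grade. Protocol Section 10.5.1 adds: "Subjects should NOT make up any missed doses". SAP Section 3.5 acknowledges that dose delays and reductions are allowed under Protocol Section 10.10, but Section 7.2.2 does not carry this into the calculation.

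**The concern.** A dose withheld for toxicity is omitted because the site followed the protocol, and it cannot be recovered later. A denominator fixed by the schedule scores that dose like one the subject skipped. The result contradicts the section's own opening idea of compliance.

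Two outputs could be affected. The study report could describe a subject who followed a safety instruction as having poor treatment compliance. And if OS is explored by compliance group, the low group could contain both non-adherent subjects and subjects held for toxicity. A survival difference could then be read as an effect of adherence when part of it reflects who became ill. SAP Section 8 plans no covariate adjustment that would separate the two.

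**Working it through.** The documents state no compliance rate for this trial, so there is no figure to reproduce. The check applies the stated rule.

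**Inputs**
- Scheduled doses: 15, one daily on Days 0 to 14 (Protocol synopsis, Dose & Schedule). If only post-resection doses are counted, 14.
- Cut-offs: 80% (SAP Section 7.2.2 and Table 2) and 100% (the alternative in the OS factor list).
- Assumptions: the same number of capsules at each dose, held capsules are returned, and no other dose is missed.

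**Rule as written in the prose of SAP Section 7.2.2:** compliance = 100 × (scheduled − held) / scheduled.

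| Doses held | Of 15 | At 80% cut | Of 14 | At 80% cut |
|---|---|---|---|---|
| 1 | 14/15 = 93.3% | compliant | 13/14 = 92.9% | compliant |
| 2 | 13/15 = 86.7% | compliant | 12/14 = 85.7% | compliant |
| 3 | 12/15 = 80.0% | compliant | 11/14 = 78.6% | non-compliant |
| 4 | 11/15 = 73.3% | non-compliant | 10/14 = 71.4% | non-compliant |

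A subject held at Day 3 who never restarts has taken Days 0, 1 and 2: 3/15 = 20.0%. One held dose is enough to fall below 100%.

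**Second formula (SAP Section 7.2.1.2):** 100 × (dispensed − not taken) / dispensed. For the subject with 4 held doses, if all 15 doses' worth was dispensed, the score is 11/15 = 73.3%. If the 4 held doses were never dispensed, it is 11/11 = 100%. The same conduct can therefore score differently depending on dispensing practice, and the OS factor list does not say which formula feeds it.

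**Held doses removed from the denominator:** 100 × taken / (scheduled − held).
- 4 held, none skipped: 11/11 = 100%, against 73.3% as written.
- 4 skipped without instruction: 11/15 = 73.3%, unchanged.
- 1 skipped and 4 held: 10/11 = 90.9%, against 10/15 = 66.7% as written.

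The revised ratio still detects true non-adherence and no longer penalises an instructed hold.

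**The case against.** The strongest reply has four parts.

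**The text can be read more kindly.** The displayed formula counts capsules prescribed per day, which could be zero on a held day, and the section speaks of following instructions. That reading is possible, but the prose beside it points to the schedule of events, and Section 7.2.1.2 offers a third option. The ambiguity is itself a reason to settle the definition.

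**Holds are visible elsewhere.** SAP Section 7.2.1.2 lists dose modifications and tabulates doses received. The planned outputs include adverse events leading to interruption (Table 14.3.1.6), veledimex dose modifications (Listing 16.2.5.3) and corticosteroid dosage (Listing 16.2.4.7). This stands: a careful reader could separate holds from skipped doses. It does not correct the compliance label.

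**A schedule-based ratio measures drug received.** That is true and useful, but it is exposure, and the SAP already tabulates doses received.

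**The OS use is thin.** There is no formal testing, and SAP Section 7.2.1.2 says only that compliance subgroups may be explored. The SAP contents list a Section 8.2.2 on exploratory OS analyses whose text is not visible, and parts of Section 10 are blacked out. How the factor is analysed, or whether it was kept, cannot be read. This stands.

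A reader might also infer that edema holds would fill the under-80% group and bias OS by a calculable amount. The documents do not support that. Notes 1, 5 and 6 to Protocol Table 2 make the table general guidance, set edema aside unless it fails maximal medical support, and describe short-term withholding at Grade 3 as something to consider. Nor can the number of subjects held be taken from the 86% transient lymphopenia rate in Protocol Section 6.4.1.1. That rate comes from a trial of another adenoviral IL-12 vector in pancreatic, colorectal and liver cancers, and it is not a rate of dose holds.

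**Conclusion.** The rule is wrong as written, and the severity is minor. By the prose of SAP Section 7.2.2, a subject who takes every permitted dose falls below 80%, and so meets the Table 2 deviation, once 4 or more of 15 doses are held (3 or more if 14 are counted). Any held dose fails the 100% cut. The SAP also carries two conflicting denominators.

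Three stronger readings are tempting and do not hold:
- That every subject who follows a hold is scored non-compliant. Holds of 1 to 3 of 15 doses remain at 80% or above.
- That the OS subgroup is biased to a known extent. A low-compliance group could mix toxicity holds with non-adherence, but the number of subjects held is not given and the analysis is exploratory and not fully visible.
- That the overall OS estimate or PP membership changes. SAP Section 4.7.2 says that in general no subject was planned to be removed for a deviation, and Table 2 does not equate a relevant deviation with a major one.

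The arithmetic assumes equal capsules per dose, return of held capsules and no other missed doses.

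**What to change.** Before database lock, use one definition in SAP Section 7.2.2 and refer to it from Section 7.2.1.2, Table 2 item 1 and the OS factor list:

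*Expected veledimex doses are the scheduled doses on Days 0 to 14 minus any dose withheld or discontinued under Protocol Section 10.10 or the Day 3 laboratory rule. Compliance (%) is doses taken divided by expected doses, times 100.*

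Delete the tablets-dispensed formula in Section 7.2.1.2. If OS by amount of drug received is explored, label the factor *veledimex doses received* and show how many subjects in each group had doses held.

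The cost is one definition and one deleted formula. No protocol amendment or new data collection is needed: the subject diary records the reason for each missed dose (Protocol Section 10.5.1), and the adverse event page records action taken with the study drugs (Protocol Section 14.6). The downside is that a subject stopped on instruction after three doses scores 3/3 = 100%, so compliance must be read beside the doses-received table already planned.

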8. EFFICACY ANALYSIS

No formal hypothesis testing will be performed for primary and secondary endpoints. Estimates of the single arm will be determined and will be compared numerically with historical control estimates, wherever applicable.

Observed data will be presented over all study centers. No imputation of values for missing data will be performed.

In general, all estimates will be calculated considering two-sided 5% level of significance. No adjustments for covariates will be made.

- See [Section 10](#) of this document for all changes to originally preplanned efficacy analyses.

8.1. Primary Efficacy Endpoint

The primary endpoint for evaluation of efficacy is the OS hazard rate which is performed by estimating the hazard rate based on the accrual and follow-up of all treated subjects. Subjects will be followed from the first date of treatment up to 2 years for overall survival.

OS is defined as the duration of time from the first dose of study drug (i.e., cemiplimab at Day - 7) to the date of death from any cause. Censoring will be considered as below:

- Subjects who discontinue study will be censored at date of discontinuation.
- Subjects who are lost to follow-up will be censored at last follow-up contact date.
- If the subject has not died, the subject is censored if still alive up to 2 years from the first dose of study drug received.

All summaries and analyses for the primary efficacy endpoint will be based on per-protocol population.

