16.6.2. Safety Analyses

The safety population will be used to perform safety evaluations for all safety variables.

Safety evaluations will be based on the incidence, intensity, and type of AEs and SAEs. Clinically significant changes in the subjects' physical examinations, vital signs, and ECG evaluations, and abnormal laboratory values will be captured as AEs. Safety will also be assessed based on medical history and prior/concomitant medications.

The safety evaluation period extends from the date the patient signs the ICF until 90 days after the last dose of study drug, unless the patient discontinues the trial due to one of the following reasons:

- Documented progression
- Symptomatic deterioration also denoted as symptomatic progression
- AEs that the investigator feels will subsequently make the subject noncompliant with the protocol planned Schedule of Study Procedures
- Loss to follow-up
- Noncompliance with the protocol
- Other reason not listed above

All treatment-emergent AEs will be coded using the Medical Dictionary for Regulatory Activities (MedDRA) and will be tabulated by number and percent of subjects, and according to relationship to the study drugs, severity, and seriousness. Treatment-emergent is defined as any AE that occurs during or after administration of the first dose of study drug through the evaluation period for safety defined above, regardless of relationship to study drug; or any event that is present at baseline that worsens in intensity or is subsequently considered to be drug related by the investigator. Deaths, SAEs, and AEs resulting in study discontinuation will be listed.

Subjects who discontinue the trial as defined above will be followed for safety up to 90 days after discontinuation and until all safety events that have started during the safety evaluation period are classified as resolved or the end of the study is reached. After the conclusion of the safety evaluation period is triggered by a discontinuation event, the subject continues to be followed only for OS.

Listings of vital signs and physical examination data will be presented by visit.

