16.6.3. Overall Survival

OS is defined as the duration of time from the first dose of study drug (Day -7) to the date of death or to the last follow-up contact date if the subject has not died, in which case the subject is censored if still alive up to 2 years from the first dose of study drug received.

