17.4. Duration of the Study

The duration of this study from the time of initiating subject enrollment until the completion of survival follow-up is anticipated to be approximately 48 months, including 24 months for enrollment and 2 years of further follow-up.

The overall duration is expected to be up to 2 years for an individual subject, including the following:

- Screening period of up to 30 days prior to dosing with Ad-RTS-hIL-12 and veledimex
- Initial Study treatment period of 3 weeks (Days -7 through 14)
- Assessment of safety through the Follow-up Period
- Assessment of tumor response at Day 57 (\pm 3 days), and every 2 months thereafter until the occurrence of confirmed tumor progression
- Survival status through 2 years

In addition, subjects who discontinue or complete study treatment without objective evidence of disease progression should continue to be followed until confirmed disease progression has been documented. Subjects will be followed for survival status for 2 years after enrollment, except for death or loss to follow-up. The active study period refers to the study period from informed consent through the Initial Follow-up Period.

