5.2. Disposition: The FAS Population

After displaying the number of subjects screened and not treated, the subject disposition presents the number of subjects in the FAS population as the starting point. All percentages will be based on the number of FAS subjects. Subsequently the table illustrates:

- The number and percent of subjects who:
 - Complete the study,
 - Discontinue from the study by reason for treatment discontinuation and study discontinuation.
- Subjects who discontinued from veledimex.
- Subjects who discontinued from cemiplimab.
- The number and percentage of subjects in each analysis population:
 - PP population and
█ ██████████.
 - If applicable, important protocol deviations will be summarized and listed.
 - Patients could be excluded from the PP population for more than one reason.

Figure 1: Patient Disposition for Protocol Defined Populations

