8.2. Primary Analysis for OS

The primary analysis for estimating the hazard rate for the time to OS denoted as the function $S(t)$ will be performed on the PP population using the Kaplan Meier (KM) Product-Limit estimation method. A secondary analysis will also be implemented for the FAS. Using the KM method:

- The median survival time along with the 95% Confidence Interval (CI) will be constructed.
- The 25Th and 75th quartile of survival time will also be provided supplemented by the Kaplan-Meier plot of OS.

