8.3.1. The OS rate at fixed timepoints 6, 12, 18 and 24 months

- OS rates will be derived from the KM estimate along with the corresponding two-sided 95% CI estimated using Greenwood's formula for the variance and the log-log transformation applied to the survivor function S(t)

8.3.2. Overall PFS and PFS rate at fixed timepoints 6, 12, 18 and 24 months

- Overall PFS and the PFS rate of pseudo-progression (PSP) will also be estimated. at month 6, 12, 18 and 24 with corresponding 95% confidence interval (CI).

PFS is defined as the duration of time from the first dose of study drug (i.e., cemiplimab at Day -7) to the confirmed progression (as determined by immunotherapy Response Assessment for Neuro Oncology (iRANO) criteria) or death from any cause, whichever occurs first. Censoring will be considered as below:

- Subjects who discontinue study without any event will be censored at date of discontinuation.
- Subjects who are lost to follow-up without any event will be censored at last follow-up contact date.
- If the subject has no progression or not died, the subject is censored if still alive up to 2 years from the first dose of study drug received.

The time to PFS will be estimated on the PP population using the Kaplan Meier (KM) Product-Limit estimation method. The median PFS will be summarized along with corresponding 95% CI. A Kaplan-Meier plot of PFS will also be provided.

Pseudo-progression (PSP) is a term used to describe the appearance of radiographic disease progression due to increase contrast enhancement on MRI without true tumor progression. The increase in contrast enhancement can be influenced by several parameters including differences in radiologic technique, the amount of contrast agent used, the timing of the contrast agent administration relative to the imaging, postsurgical changes, infarction, treatment related inflammation, seizure activity, sub-acute radiation effects, radiation necrosis, and corticosteroid use. Consideration of these factors by experts and clinical experience is likely to identify these subjects.

Number and proportion of subjects with PSP will be summarized with corresponding two-sided 95% confidence interval (CI).

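### SAP 8.1 censors overall survival at study discontinuation with no exception for recorded deaths, against protocol 16.6.2, 16.6.3 and 17.4

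*SAP*

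**What the plan says.** SAP 8.1 defines OS from the first cemiplimab dose "to the date of death from any cause" and then lists three censoring rules. The first is "Subjects who discontinue study will be censored at date of discontinuation". The second censors subjects lost to follow-up at their last contact, and the third censors survivors at 2 years.

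The protocol's rule is different:

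- Section 16.6.3 measures OS "to the date of death or to the last follow-up contact date if the subject has not died", with survivors censored at up to 2 years.
- Section 16.6.2 lists reasons for leaving the trial, among them documented progression, symptomatic deterioration, adverse events and noncompliance. It then says: "After the conclusion of the safety evaluation period is triggered by a discontinuation event, the subject continues to be followed only for OS".
- Section 17.4 says: "Subjects will be followed for survival status for 2 years after enrollment, except for death or loss to follow-up".

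Two other parts of the SAP bear on the reading. The matching PFS rule in Section 8.3.2 carries a qualifier: "Subjects who discontinue study without any event will be censored at date of discontinuation". The disposition table in Section 5.2 names two kinds of discontinuation: "Discontinue from the study by reason for treatment discontinuation and study discontinuation".

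**The concern.** The SAP adds a censoring event that the protocol does not have, and nothing in the wording lets a recorded death take precedence over it. Loss to follow-up has its own rule, so the discontinuation rule must apply to other subjects. On the protocol's use of the term, these include subjects who leave because their disease has worsened and who are still being followed for survival.

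Censoring those subjects removes people at higher risk of death from the risk set. Kaplan-Meier assumes that censored subjects have the same prognosis as those who remain, so the curve would be biased upwards and the hazard downwards. This is a single-arm trial whose OS estimate is compared numerically with historical estimates (SAP Section 8), so the error would favour the treatment and no control arm would share it. The term is also undefined, so two programmers could derive different primary results from the same data.

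**Working it through.** **1. The texts compared.**

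| Situation | Protocol | SAP 8.1 as written |
|---|---|---|
| Leaves the trial at progression, later dies, death recorded | Event at death (16.6.2, 16.6.3) | Censored at discontinuation |
| Leaves the trial, alive at last contact | Censored at last contact (16.6.3) | Censored at discontinuation |
| Lost to follow-up | Censored at last contact | Censored at last contact |
| Alive at 2 years | Censored at 2 years | Censored at 2 years |

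The first two rows differ. The first loses events, and the second loses observed survival time.

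**2. Other safeguards.** SAP 8.2 adds an FAS analysis ("A secondary analysis will also be implemented for the FAS"), but the readable text gives no other OS censoring rule for it. The readable part of SAP Section 10 lists no change to OS censoring.

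**3. The plan's own OS figure.** The only precision stated for OS is a binomial standard error of about 10% for 25 to 30 subjects. It reproduces: √(0.5 × 0.5 / 25) = 0.100 and √(0.5 × 0.5 / 30) = 0.091. It does not depend on the censoring rule, so it neither reveals nor limits the problem.

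**4. Illustration of size.** From the documents (protocol 6.1): median OS 6 to 7 months and median PFS 2 to 3 months in recurrent disease. From protocol 13.1: progression is confirmed 12 weeks after it is first seen (84 days, or 84 / 30.4375 = 2.76 months). Assumed, because the documents are silent: 15% of first events are deaths; 10, 25 or 50% of progressors are recorded as discontinued; all times are exponential; the 8-week scan interval is ignored.

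With λ = ln 2 / 2.5 = 0.277 per month, q = 0.15 and mean post-progression survival μ,

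S(t) = e^(−λt) + (1 − q) λ [e^(−t/μ) − e^(−λt)] / (λ − 1/μ).

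Setting S(7) = 0.5 gives μ ≈ 6.0 months. The hazard of death is then 0.15 × 0.277 = 0.042 per month before progression and 1 / 6.0 = 0.17 after it, about four times as high. Censoring at progression removes the high-risk group.

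Simulating at least 400,000 subjects per scenario, with follow-up cut at 24 months:

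| Progressors censored | KM median (all deaths counted: 7.0) | Hazard lower by | Deaths lost, of about 24 per 25 subjects |
|---|---|---|---|
| 10%, at progression | 7.15 | 3% | 2 |
| 25%, at progression | 7.4 | 8% | 5 |
| 50%, at progression | 8.1 | 19% | 10 |
| 10%, 12 weeks later | 7.04 | 2% | 1 |
| 25%, 12 weeks later | 7.1 | 4–5% | 3 |
| 50%, 12 weeks later | 7.3 | 10% | 6 |

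Over OS medians of 6 and 7 and PFS medians of 2, 2.5 and 3 months, the median rises by 0.1 to 1.5 months with no lag and by 0.03 to 0.34 months with the 12-week lag.

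**5. Discontinuation unrelated to prognosis.** With 10, 25 or 50% of all subjects censored at a uniform time over 0 to 24 months, the median stays at 7.0. Precision is lost but there is no systematic bias.

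**6. One trial of 25, with 25% of progressors discontinued.** Over 4,000 simulated trials, the median was higher than with all deaths counted in about 55% and lower in about 14–15% (no lag), or in about 33–34% and 14–15% (12-week lag).

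**The case against.** The best defence is that this is loose drafting. Censoring rules are ordinarily applied to subjects without the event, and the loss-to-follow-up rule also lacks an if-alive qualifier. SAP 5.2 separates stopping treatment from stopping the study, so study discontinuation may mean only leaving survival follow-up. Protocol 9.4 lets a subject or investigator end participation at any time, so full withdrawal is a real exit besides loss to follow-up. The reasons in protocol 16.6.2 sit in a safety section that SAP 8.1 does not cite. The effect is assumed, and with the 12-week lag it is small beside sampling error: under an exponential model with 24 deaths, a 7-month median has a 95% interval of about 7 × exp(±1.96/√24), or 4.7 to 10.4 months. There is no formal test, and the planned listings of survival, censoring times and deaths would let a reader spot the affected subjects.

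Much of this stands. The narrower reading is possible and would make the effect small. Section 8.2.2 (exploratory OS analyses) appears in the contents but not in the readable text, and parts of Section 10 are redacted, so the absence of another rule can be claimed only for what is readable.

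It does not remove the conflict. Even on the narrower reading, an unqualified rule overrides a recorded death that the protocol counts. The PFS rule shows that the authors had the qualifier available. Wide sampling error does not excuse a directional bias, and listings do not correct the estimate.

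**Conclusion.** The concern holds. SAP 8.1 as written conflicts with the protocol's OS definition and follow-up, and it leaves a deciding term undefined for the primary endpoint. It should be fixed before OS is derived.

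The direction, an OS estimate that is too favourable on average, rests on discontinuation being related to worsening disease; the reasons in protocol 16.6.2 make that likely. The size is unknown. In the illustration it runs from negligible (0.03 months, with few discontinuations and a 12-week lag) to 1.5 months (half of progressors censored at progression). Those figures depend on the assumed discontinuation fractions, lag, share of first events that are deaths, and exponential times. If discontinuation is unrelated to prognosis, or means only leaving survival follow-up, little or no systematic bias follows.

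**What to change.** Replace the first OS censoring rule in SAP 8.1 with text such as: *Every recorded death within 2 years of first dose is an event, regardless of treatment or study status. Subjects not known to have died are censored at the last date known alive, capped at 2 years.* For a subject in follow-up, that date is the protocol's last follow-up contact.

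Define study discontinuation, and report how many recorded deaths fall after it. If censoring at discontinuation is kept at all, label it as a sensitivity analysis.

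The cost is one SAP rule and a minor change to the time-to-event derivation. No new data are needed, because the protocol already collects survival status for 2 years. The reported median may become less favourable. If the narrower meaning was intended all along, the results will hardly change and the ambiguity is gone.
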